2.2 Violations and deviations

Important protocol deviations will be agreed by the study team physician, pharmacokineticist and statistician before any statistical analysis is performed.

Patients who withdraw from the study following dosing, but prior to study completion, will be included in the PK analysis provided they have evaluable profiles over the planned collection period. Patients with partial data will be evaluated on a case-by-case basis to determine if sufficient data are available for meaningful analysis.

If a patient vomits within approximately 3 hours after dosing with olaparib tablets, all PK sampling may be omitted for that treatment period but the safety assessments should continue as per the study schedule. The patient may continue in the study and proceed with Part A, if applicable, and then on to Part B and Part C.

Important protocol deviations include changes to the procedures that may impact the quality of the data, or any circumstances that can alter the evaluation of the PK. Examples include,

but may not be limited to, vomiting following oral dosing occurring within the time frame of 2 times the median t_{\max} , sample processing errors that lead to inaccurate bioanalytical results, incomplete dose administered, incomplete PK profile collected, and/or use of disallowed concomitant medication. In the case of an important protocol deviation, affected PK data collected will be excluded from the summaries and statistical analyses, but will still be reported in the study result listings. Important deviations will be listed and summarised in the Clinical Study Report (CSR).

3. PRIMARY AND SECONDARY VARIABLES

Primary variables

The primary PK outcome variables to be calculated for olaparib are described below. All PK parameters for Parts A & B will be summarised descriptively. For Part A, AUC, (or AUC_{0-t} , if AUC is not adequately estimable), C_{\max} and t_{\max} will also be statistically analysed.

- Single-dose PK parameters will be calculated for olaparib during each treatment period in Part A:
 - C_{\max} Maximum plasma concentration obtained directly from the observed concentration versus time data
 - t_{\max} Time to maximum plasma concentration obtained directly from the observed concentration versus time data
 - AUC_{0-t} Area under the plasma concentration-time curve from zero to the time of the last measurable concentration, calculated by linear up/log down trapezoidal summation
 - λ_z Terminal rate constant estimated by log-linear least squares regression of the terminal part of the concentration-time curve
 - AUC Area under the plasma concentration-time curve from zero (pre-dose) extrapolated to infinity calculated by linear up/log down trapezoidal summation and extrapolated to infinity by the addition of the last quantifiable concentration divided by the terminal rate constant: $AUC_{0-t} + C_{\text{last}}/\lambda_z$
 - $t_{1/2}$ Terminal half-life. Visual assessment will be used to identify the terminal linear phase of the concentration-time profile
 - CL/F Apparent plasma clearance
 - V_z/F Apparent volume of distribution
- Multiple-dose PK parameters will be calculated for olaparib on Day 5 of Part B:

- $C_{ss,max}$ Maximum plasma concentration obtained directly from the observed concentration versus time data
- $t_{ss,max}$ Time to maximum plasma concentration obtained directly from the observed concentration versus time data
- $C_{ss,min}$ Minimum plasma concentration obtained directly from the observed concentration versus time data
- $t_{ss,min}$ Time to minimum plasma concentration obtained directly from the observed concentration versus time data
- $AUC_{0-\tau}$ Area under the plasma concentration-time curve over the dosing interval, τ , calculated by linear up/log down trapezoidal summation
- $C_{ss,avg}$ Average concentration over the dosing interval calculated as $AUC_{0-\tau}/\tau$
- FI Fluctuation index, calculated as $[(C_{ss,max}-C_{ss,min})/C_{ss,avg}]\times 100\%$
- CL_{ss}/F Apparent plasma clearance

The PK analysis of the plasma concentration data for olaparib will be done at AstraZeneca R&D. The actual sampling times will be used in the final PK parameter calculations, except for the pre-dose sample for which the time will be set to zero. All PK computations will be performed using Phoenix™ for WinNonlin. Additional PK parameters may be determined if deemed appropriate.

Secondary variables

The pharmacodynamic (PD) analyses of the dECG data will be performed by ERT, with the exception of the derivation of QTcI (Quintiles will derive QTcI as described below). ERT standard operating procedures (SOPs) and Work Instructions will be used as the default methodology if not otherwise specified.

- Pharmacodynamic (PD) variables i.e. ECG intervals (including QT and QTc interval) will be reported based on the continuous dECG measurements:
 - RR
 - HR
 - PR
 - QRS

– QT

The QT interval will be corrected for RR (the duration of a heart beat) to obtain corrected (QTc) variables:

- QTcF (Fridericia correction)
- QTcB (Bazett correction)
- QTcI (Individual correction)

The general formula for QTc that will be used is:

$$QTc = QT / RR^b$$

with the QT intervals expressed in milliseconds and the RR interval in seconds.

Different factors for b in the formula above will be used:

- (i) For QTcF $b=1/3$
- (ii) For QTcB $b=1/2$
- (iii) For QTcI individual values of b_i will be estimated for each patient from the study data.

For the estimates of the individual-specific correction factors, the estimate of individual slopes, b_i , a fixed effects linear model for patient i , part p , and time point t will be used:

$$\log(QT_{i,p,t}) = a_{i,p} + b_i \log(RR_{i,p,t})$$

The corrected QT is then obtained by:

$$QTcI_{i,p,t} = QT_{i,p,t} / (RR_{i,p,t})^{b_i}$$

The estimation will be based on the pooled data from the drug-free days: Day -1 in Part A, and Day -1 in Part B.

Additional methods of QT correction may also be applied.

To obtain a single PD value at each specified time point, the mean of the triplicate values at that time point will be used.

For change from baseline (pre-dose): Baseline is defined as the pre-dose measurement taken on the same day that the post-dose measurements are taken. This also applies to Day -1 in Part A and Part B, despite no dose being administered.

For change from baseline (time-matched day -1): Baseline for the PD data in Part A is defined as Day -1 of treatment period 1 in Part A, and baseline for the PD data in Part B is defined as Day -1 in Part B. For each patient, the change-from-baseline in a PD variable at each time point will be calculated as the difference between the mean of the replicate value at each post-dose time point and the mean of the time-matched replicate value at the corresponding baseline.

- Safety and tolerability will be assessed by:
 - Assessment of adverse events (AEs), graded by [CTCAE](#) (v4.03)
 - Physical examination
 - Vital signs (including BP and pulse)
 - Standard 12 lead ECGs
 - Evaluation of laboratory parameters (clinical chemistry, haematology, and urinalysis)

Adverse events (AEs) will be classified according to the terminology of Medical Dictionary for Regulatory Activities (MedDRA), Version 16. AEs will also be assigned a maximum CTC grade by the Investigator.

Each adverse event will be assigned to the period of the study in which they started as follows: The baseline period is the time between enrolment into the study and receipt of the first dose of study treatment. The treatment period is the time between receipt of the first dose of study drug and the follow-up assessment at the end of the study. The treatment period is divided into Part A, Part B and Part C, with Part A being subdivided according to which food condition study treatment was received under. AEs occurring in the baseline period will be listed only and will not be included in any summary tables.

Table 1 Adverse event occurrence

Adverse event occurrence	Period assigned	Study treatment (food condition)
Date and time before first treatment with olaparib	Baseline period	Not applicable
Date and time the same as or greater than the date and time of the first treatment with olaparib but before date and time of second treatment	Treatment period 1 (Part A)	Fed [OR] Fasted, dependent on treatment sequence
Date same as or greater than date of first treatment with olaparib but prior to date of second treatment; but time is missing	Treatment period 1 (Part A)	Fed [OR] Fasted, dependent on treatment sequence
Date and time the same as or greater than the date and time of the second treatment with olaparib, but prior to the date and time of Part B treatment, or up to (and including) 30 days after the last dose date (where the patient does not enter Part B)	Treatment period 2 (Part A)	Fed [OR] Fasted, dependent on treatment sequence
Date same as or greater than date of second treatment with olaparib, but prior to the date and time of first Part B treatment, or up to (and including) 30 days after the last dose date (where the patient does not enter Part B); but time is missing	Treatment period 2 (Part A)	Fed [OR] Fasted, dependent on treatment sequence
Date and time the same as or greater than the date and time of the first Part B treatment with olaparib, but prior to the date of optional Part C treatment, or up to (and including) 30 days after the last dose date (where the patient does not enter Part C)	Part B	Olaparib 300 mg bd
Date same as or greater than date and time of first Part B treatment with olaparib, but prior to the date of optional Part C treatment, or up to (and including) 30 days after the last dose date (where the patient does not enter Part C); but time is missing	Part B	Olaparib 300 mg bd
Date same as or greater than start date of optional Part C treatment with olaparib (time not recorded in Part C), up to (and including) 30 days after the last dose date	Part C	Olaparib

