Part B of this study is an open-label study in the same patients who participated in Part A. Upon completion of Part A, following a washout period (of at least 5 days and no more than 14 days between the last dose in Part A and Day -1 of Part B) and providing the patient continues to meet the study entry criteria, each patient will receive olaparib tablets 300 mg bd for 5 days. Patients will check into the clinic on the evening of Day -2. On Day -1, baseline dECG assessments will be performed at clock times matched to planned/scheduled dECG assessment times on Day 5. Patients will be discharged from the clinic on the evening of Day -1. Patients will self-administer their olaparib doses under fasted conditions (from 1 hour prior to 2 hours after the olaparib dose) from Day 1 up to the morning of Day 4 on an outpatient basis. On the evening of Day 4, patients will check back into the clinic, and will receive their Day 4 evening dose. On the morning of Day 5, patients will receive their Day 5 morning dose after an overnight fast and will remain fasting for 4 hours post-dose. Patients will undergo dECG and PK assessments pre-dose and for 12 hours post-dose. The dECGs performed on Day 5 will be clock-matched to the actual times that the Day -1 dECGs are performed. Patients will be discharged from the clinic after completing 12-hour assessments on Day 5, and will self-administer their evening Day 5 dose of olaparib tablets. On Day 5 of Part B patients should be fasted over the same time period as Day -1.

On completion of Part B, patients may be entered into Part C and continue to take olaparib tablets (300 mg bd) if they and the investigator agree that this is appropriate. Patients should start Part C immediately after the last dose received in Part B. Patients will have weekly clinic visits for the first 4 weeks; thereafter visits will be every 4 weeks. Part C will be of 12 months' duration from the date the last patient enters this part of the study.

During and after Part C, patients may continue to take olaparib tablets. After the end of Part C patients will be seen as per their normal routine clinical schedule and no clinical data will be collected, other than serious adverse events (SAEs) and drug dispensing/accountability.

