4.2.4 Pharmacodynamic parameters (Parts A & B)

All data received will be presented in data listings. Pharmacodynamic summaries will be presented for patients in the QT analysis set by treatment and study day for Part A, and study day for Part B. Data from patients excluded from the QT analysis set will be included in the data listings, but not in the summaries. Extra measurements (such as unscheduled or repeat assessments) will not be included in summary tables, but will be included in patient listings.

The PD variables (absolute values and change from baseline (pre-dose)) will be listed and summarised using descriptive statistics (n, mean, SD, median, minimum, and maximum). Change from baseline (time-matched day -1) in PD variables will also be listed. The QT/QTc outliers are defined as QT/QTc values following dosing that are greater than 450 ms or are increases from baseline (pre-dose) greater than 30 ms. QT/QTc outliers will be highlighted in the data listings and summarised using the following categories:

- values that are
 - >450 ms
 - >480 ms
 - >500 ms

and

- Values that are increases from baseline (pre-dose) of

- >30 ms
- >60 ms
- >90 ms

Box-plots of QTcB, QTcF and QTcI will be presented for absolute values and change from baseline (pre-dose), separately for Part A and Part B.

Patient profile plots of RR, HR, PR, QRS, QT, QTcB, QTcF and QTcI will be presented for absolute values and change from baseline (both pre-dose and time-matched day -1), separately for Part A and Part B.

The number and percentage of patients who meet the ECG outlier criteria at any assessment after start of investigational product (IP) will be tabulated by treatment for Part A (“Fed (A)” and “Fasted (A)”), and by study day for Part B (“Day -1 (B)” and “Day 5 (B)”).

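### Part B: the summarised QT/QTc change and the >30/>60/>90 ms counts are measured from the Day 5 pre-dose value, an on-treatment trough, so any effect still present at trough is subtracted out

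*SAP*

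**What the plan says.** SAP Section 3 (secondary variables) defines two changes from baseline for the digital ECG variables.

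- **Same-day pre-dose.** "Baseline is defined as the pre-dose measurement taken on the same day that the post-dose measurements are taken". The same rule is applied to each Day -1, although no dose is given then.
- **Time-matched Day -1.** For this change, "baseline for the PD data in Part B is defined as Day -1 in Part B", and each post-dose value is compared with the Day -1 value at the same clock time.

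Section 3 regards Day -1 as free of drug. On the individual QT correction it says: "The estimation will be based on the pooled data from the drug-free days: Day -1 in Part A, and Day -1 in Part B".

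Section 1.2 gives the Part B timetable. Dosing is twice daily from Day 1 ("each patient will receive olaparib tablets 300 mg bd for 5 days"). On the evening of Day 4, "patients will check back into the clinic, and will receive their Day 4 evening dose". On Day 5, "Patients will undergo dECG and PK assessments pre-dose and for 12 hours post-dose". The drug-free reference is collected on purpose: "On Day -1, baseline dECG assessments will be performed at clock times matched to planned/scheduled dECG assessment times on Day 5".

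Section 4.2.4 then assigns the two changes to outputs. The pre-dose change goes into the descriptive summaries, the change box-plots and the outlier rule ("increases from baseline (pre-dose) greater than 30 ms"), with categories at >30, >60 and >90 ms. The time-matched change is listed and appears in patient profile plots. It enters no summary table and no count.

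**The concern.** Part B exists to describe the QT effect of repeated dosing, which is half of the QTc secondary objective in Section 1.1. The reference for its change tables is an on-treatment reading. If QTc is still prolonged 12 hours or so after the Day 4 evening dose, that prolongation is in the reference as well as in the post-dose values, and it drops out of the difference. The tables would then show less effect than there is, and patients with a real increase above a cut could go uncounted.

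The plan's parts also do not fit together. Section 2.1 admits a patient to the QT analysis set on the strength of one evaluable value time-matched with Day -1. It does not ask for a Day 5 pre-dose value. A patient can thus qualify on a comparison that is never summarised, and contribute nothing to the change tables that are.

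Section 4.1 says that the sponsor expects regulatory questions about QT, so these outputs are likely to be used.

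**Working it through.** The SAP states no QTc effect size, SD, margin or power, so there is no planned figure to reproduce. The check is a trace of the baseline, followed by an illustration with labelled assumptions.

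**1. What the Day 5 pre-dose value is.** Four days (Days 1 to 4) at two doses a day gives 4 × 2 = 8 planned doses before it, the last on the evening of Day 4 (Section 1.2).

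**2. What each change measures.** Let q(t) be a patient's drug-free QTc at clock time t, and e(t) the drug effect on Day 5, with t = 0 for pre-dose.

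- Time-matched change: [q(t) + e(t)] − q(t) = e(t).
- Pre-dose change on Day 5: [q(t) − q(0)] + [e(t) − e(0)].
- Pre-dose change on Day -1: q(t) − q(0).

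Setting Day -1 beside Day 5 in the change tables removes the within-day drift q(t) − q(0) and leaves e(t) − e(0). The trough effect e(0) is still lost.

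**3. Size.** Write D = e(t) and r = e(0)/D, and set drift aside. The reported change is D(1 − r), and the true rise needed to exceed a cut c is c/(1 − r). The values of r are assumed.

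| r | True 35 ms reads as | Needed for >30 | Needed for >60 | Needed for >90 |
|---|---|---|---|---|
| 0 | 35 ms | 30 ms | 60 ms | 90 ms |
| 0.10 | 31.5 ms | 33.3 ms | 66.7 ms | 100 ms |
| 0.25 | 26.25 ms | 40 ms | 80 ms | 120 ms |
| 0.40 | 21 ms | 50 ms | 100 ms | 150 ms |

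A patient with a true 35 ms rise leaves the >30 ms class once r reaches 1 − 30/35 = 0.14. A 65 ms rise leaves the >60 ms class at r = 1 − 60/65 = 0.08, and a 95 ms rise leaves the >90 ms class at r = 1 − 90/95 = 0.05.

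**4. Effect on a count.** Take the 42 evaluable patients of Section 1.2. Assume a mean D of 20 ms and normally distributed changes with SD 10 ms. The expected number above 30 ms at one time point is 42 × [1 − Φ((30 − 20(1 − r))/10)].

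- r = 0: 42 × 0.1587 = 6.7. This is also the count against Day -1.
- r = 0.10: 42 × 0.1151 = 4.8.
- r = 0.25: 42 × 0.0668 = 2.8.
- r = 0.40: 42 × 0.0359 = 1.5.

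Between r = 0 and r = 0.40 the count falls from 4.4 to 0.5 with an assumed SD of 8 ms, and from 8.5 to 2.8 with 12 ms.

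**5. What is not affected.** Section 4.2.4 also summarises absolute values by study day in Part B, box-plots absolute QTcB, QTcF and QTcI, and counts >450, >480 and >500 ms for Day -1 and Day 5. None of these uses a baseline. If the same patients contribute on both days, the Day 5 mean minus the Day -1 mean at a clock time equals the mean time-matched change.

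**The case against.** The strongest reply is that the plan does not hide a sustained effect. Absolute QTc is summarised on both days at matched clock times, so a reader can subtract the means and recover the average effect. The absolute outlier categories are intact, and the time-matched change is available patient by patient in listings and plots. All of this stands. A reader might infer that a sustained shift would be invisible in the Part B outputs as a whole; the SAP does not support that. What the absolute tables cannot give is the SD of the paired change, or the number of patients whose QTc rose by more than 30, 60 or 90 ms from a drug-free value.

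Second, nothing in the SAP shows that a QTc effect exists or lasts to trough. This also stands. If r = 0, nothing is lost. A reader might take the figures above for an estimate of bias in this trial, but they only show how the mechanism works.

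Third, QTc is a secondary objective, the QT analysis here is descriptive, and Section 4.1 announces a separate pooled analysis with its own methods. This limits the consequences: the food-effect conclusion is untouched. The baseline of the pooled analysis is not stated, however, and that analysis does not alter the tables planned here.

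Finally, a reader might infer that the same-day pre-dose baseline is equally wrong in Part A. It is not. There the pre-dose value comes before any dose or after a washout of at least 5 days (Section 1.2). Part A has one Day -1, in period 1, so for period 2 the same-day value is the nearer drug-free reference.

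**Conclusion.** The point holds for Part B, and for the change-based outputs only: the summarised QT/QTc change, the change box-plots, the >30 ms outlier definition and the >30/>60/>90 ms categories. Their reference is a trough value after up to eight doses. They are biased towards no effect whenever some QTc prolongation persists at trough, by the fraction r of the true rise.

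The size cannot be fixed from the SAP. Over an assumed r of 0 to 0.4 the loss is 0% to 40%. The figures rest on that range, on the assumed rises and SDs, and on setting within-day drift aside.

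**What to change.** In Section 4.2.4, for Part B only, base the descriptive change summaries, the change box-plots, the >30 ms outlier definition and the >30/>60/>90 ms categories on the time-matched Day -1 (B) change already defined in Section 3. Keep the change from Day 5 pre-dose as a supportive description of movement within the dosing interval, and label it so. The increase-category rows then apply to Day 5 alone, since Day -1 becomes the reference; the absolute categories can still be shown for both days. Leave the Part A pre-dose baseline as it is.

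The cost is SAP wording, table and figure shells, and the matching programming. The Day -1 recordings are already scheduled and the time-matched change is already derived for the listings. The change should be made before the Parts A and B database lock described in Section 4.1, and before any earlier analysis of available data run to answer regulatory questions.

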1.2 Study design

This is a 3-part study in patients with advanced solid tumours:

- Part A will determine the effect of food on the PK of olaparib and the effect of olaparib on the QT interval following a single oral dose of olaparib tablets;
- Part B will determine the effect of olaparib on the QT interval following multiple oral dosing of olaparib tablets;
- Part C will allow patients continued access to olaparib tablets after the PK and QT phases (Parts A & B) and will provide for additional safety data collection.

A total of 48 patients are planned to be enrolled at approximately 8 sites in Western Europe; approximately 42 evaluable patients will be expected to complete the study.

Part A of this study is a randomised, open-label, 2-treatment period crossover study in approximately 48 patients with advanced solid tumours. Each patient will receive a single oral dose of olaparib tablets 300 mg in each of 2 treatment periods (once in the overnight fasted state and once immediately following a high-fat meal at breakfast time), with at least 5 and no more than 14 days (washout) between doses. Digital ECG (dECG), PK assessments, and safety assessments will be obtained for up to 72 hours post-dose in each treatment period. Additionally, during the first treatment period, patients will undergo baseline dECG assessments on Day -1 (ie, the day prior to dosing) at clock times matched to planned/scheduled dECG assessment times on the dosing day (Day 1). Patients will check into the clinic on the evening of Day -2 (first treatment period) or the evening of Day -1 (second treatment period) and remain resident until 24 hours after each dose of olaparib tablets (Day 2). The dECGs performed on Day 1 in each treatment period will be clock-

matched to the actual times that the Day -1 dECGs are performed in the first treatment period. Patients will return to the clinic for assessments on Days 3 and 4 of each treatment period. On Day 1 of Part A patients should be fasted over the same time period as Day -1.

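### Part A's same-day pre-dose QT baseline leaves any dECG on Days 2 to 4 without a pre-dose change, so it cannot enter the increase-from-baseline summaries or the >30, >60 and >90 ms categories

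*SAP*

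**What the plan says.** - **Baseline rule.** SAP Section 3 (secondary variables), on the pre-dose change: "Baseline is defined as the pre-dose measurement taken on the same day that the post-dose measurements are taken". It extends the rule to one kind of undosed day only, Day -1 of Parts A and B.
- **Dosing and follow-up in Part A.** Section 1.2: "Each patient will receive a single oral dose of olaparib tablets 300 mg in each of 2 treatment periods". It also says: "Digital ECG (dECG), PK assessments, and safety assessments will be obtained for up to 72 hours post-dose in each treatment period". Patients are resident until 24 hours after each dose (Day 2), and then: "Patients will return to the clinic for assessments on Days 3 and 4 of each treatment period".
- **Part B.** Section 1.2, for Day 5: "Patients will undergo dECG and PK assessments pre-dose and for 12 hours post-dose".
- **What uses the baseline.** Section 4.2.4: "The PD variables (absolute values and change from baseline (pre-dose)) will be listed and summarised using descriptive statistics". Outliers are "QT/QTc values following dosing that are greater than 450 ms or are increases from baseline (pre-dose) greater than 30 ms", with further steps at 480 and 500 ms for values and at 60 and 90 ms for increases. The outlier table covers every assessment once study drug has been started, and in Part A is split by food condition.
- **Second baseline.** Section 3 also defines a time-matched change against Day -1. Section 4.2.4 lists it and shows it in patient profile plots, but does not summarise it or use it for outliers.

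**The concern.** The baseline rule assumes that every post-dose reading shares a calendar day with a dose. That is true of Day 1 in Part A and of Day 5 in Part B. It is not true of Part A Days 2 to 4, when no dose is given. The increase-based outlier criteria therefore cannot be applied over the scope that Section 4.2.4 sets for them.

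The text leaves at least three ways to program a Day 2 to 4 reading:

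1. leave the change missing, as the words require;
2. use that period's Day 1 pre-dose value;
3. by analogy with Day -1, use the first reading of the day. A single reading on that day would then be its own baseline, and its change would be zero by definition.

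These give different tables. The effect of a single dose on QTc is a secondary objective (Section 1.1), and the sponsor expects regulatory questions on QT (Section 4.1), so the derivation should not be left open.

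**Working it through.** The plan states no figure to reproduce here. The check is a day count, followed by a sort of the planned outputs.

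**Step 1: which readings lack a same-day pre-dose value.** Inputs: one dose on Day 1 and follow-up to 72 hours (Section 1.2). Assumption: a dose between 07:00 and 10:00, because the SAP implies a morning dose without giving a clock time. For dose hour h and reading time t in hours, study day = 1 + floor((h + t)/24).

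| t (hours) | h = 7 | h = 10 | Same-day pre-dose value? |
|---|---|---|---|
| 0 to 12 | Day 1 | Day 1 | Yes |
| 24 | Day 2 | Day 2 | No |
| 48 | Day 3 | Day 3 | No |
| 72 | Day 4 | Day 4 | No |

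Part B dECGs run from pre-dose to 12 hours on Day 5, so each has a same-day pre-dose value.

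**Step 2: which outputs need the pre-dose baseline** (Section 4.2.4).

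| Output | Needs it? | Part A Days 2 to 4 under the literal rule |
|---|---|---|
| Summaries and plots of absolute values | No | Kept |
| >450, >480, >500 ms | No | Kept |
| Summary, box-plots and profile plots of pre-dose change | Yes | Lost |
| >30, >60, >90 ms increase | Yes | Lost |

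So 3 of 6 outlier categories are affected.

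**Step 3: what could be missed.** A late reading at or below 450 ms that rose by more than 30 ms appears in no outlier category under the literal rule. This needs a pre-dose value below 450 - 30 = 420 ms. For rises above 60 and 90 ms, the pre-dose value must be below 390 and 360 ms. For a late reading above 450 ms, the value is counted but the size of the rise is not.

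**Step 4: whether another rule fills the gap.**

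- Section 4.2.5 takes the last non-missing pre-dose value as baseline, but for safety variables. The dECG analysis is in Section 4.2.4.
- Section 4.1 bars imputation of missing data unless the study team agrees.
- The time-matched change feeds no summary or outlier table. Section 2.1 defines Part A time-matching, for the QT analysis set, between Day -1 and Day 1 only.

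**Step 5: number of readings.** Readings = late time points × 2 periods × patients. The time points are assumed, with full attendance.

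- 24 hours only: 1 × 2 × 42 = 84, to 1 × 2 × 48 = 96.
- 24, 48 and 72 hours: 3 × 2 × 42 = 252, to 3 × 2 × 48 = 288.
- No dECG after Day 1: 0. Section 1.2 would then be wrong about dECGs.

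**The case against.** The strongest reply is that this is loose wording that a sensible programmer would repair. Each Part A period has one dose, so the obvious reference is that period's Day 1 pre-dose value, and nothing in the SAP says that late readings are excluded. The wide scope of the outlier table also favours including them. This stands in part: exclusion is inferred from the literal rule. But the rule is explicit, it names Day -1 as the undosed day it extends to, and no other provision overrides it for dECGs. Section 3 makes the ECG vendor's procedures the default only where nothing else is specified, and here something is.

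A second reply is that dECGs on Days 2 to 4 are not established. The 72-hour sentence covers dECG, PK and safety assessments together, the specific Part A dECG statements concern Day -1 and Day 1, and the purpose of the Day 3 and 4 visits is not given. This stands as a limit on size. It does not remove the conflict, because dECG is named in that sentence.

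A reader might also infer that late readings vanish from the outlier tables, or that late QT effects would go unseen. The SAP does not support either. The three absolute categories and the absolute-value summaries and plots keep these readings, all data are listed, and values above 450 ms are highlighted. Nor do the readings lack every baseline, since the time-matched Day -1 definition is not tied to the same day.

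**Conclusion.** The point holds in a limited form. Under the rule as written, any Part A dECG on Days 2 to 4 has no pre-dose change and cannot be classed as a rise above 30, 60 or 90 ms. That conflicts with the scope that Section 4.2.4 gives the outlier table. Half of the outlier categories and the pre-dose change outputs are affected; absolute-value outputs and Part B are not.

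The conclusion rests on the 72-hour statement applying to dECGs and on a literal reading of the baseline rule. The count of 84 to 288 readings rests on assumed time points and should not be quoted as the plan's own figure. It is a number of possible readings. It is not evidence of bias or of missed events. The problem is modest, but it bears on a secondary objective and is cheap to remove.

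**What to change.** 1. In Section 3, define the Part A pre-dose baseline as the Day 1 pre-dose measurement of the same treatment period, for all later dECGs in that period. Leave the Part B and Day -1 rules as they are.
2. In Section 4.2.4, state that these readings enter the pre-dose change summaries and the >30, >60 and >90 ms counts.
3. For the time-matched change on Days 2 to 4, use the Day -1 reading at the same clock time where one exists. Readings at 24, 48 and 72 hours would fall at the clock time of the dose, so the Day -1 reading in the pre-dose slot is the natural match.
4. If no dECG is scheduled after Day 1, correct the 72-hour statement in Section 1.2 instead; items 1 to 3 are then unnecessary.

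The cost is a sentence or two of text and one derivation. No new data are needed.
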